10.3.2. Interim Analysis

No interim efficacy analyses are planned.

10.4. Key Elements of Analysis Plan

All hypothesis tests and confidence intervals will be 2-sided at an alpha level of 5%.

For statistical analysis, center information will be pooled by geographical region or size. The method of grouping by center will be agreed upon prior to unblinding the study and outlined in the Statistical Analysis Plan (SAP).

All efficacy and safety measures over the course of the study will be presented. Continuous data will be summarized by means, SDs, medians, maximum, minimum, and number of subjects. Categorical data will be summarized by counts and percentages.

10.4.2. Secondary Efficacy Analyses

Cognition and other efficacy endpoints:

- ADAS-Cog-13 scores change from baseline at Week 24
- CIBIC+ scores at Week 24
- NPI scores change from baseline at Week 24
- The DS change from baseline at Week 24
- Comparison of RVT-101 versus placebo for the above endpoints will be performed using a mixed model for repeated measures or analysis of covariance (ANCOVA), similar to the models described for the primary endpoint.

The relationship between endpoints and demographics/baseline characteristics will be investigated. The comparisons may be repeated by selected subgroups of interest, i.e., gender,

baseline severity based on MMSE score, and other baseline characteristics. Further details will be given in the SAP.

In addition, the between treatment comparisons on CIBIC+ based on the Week 24 Observed Case (OC) and Week 24 LOCF datasets using Cochran-Mantel-Haenszel test will be performed. The number and percentage of subjects in each category of CIBIC+ will also be summarized by visit for each treatment group.

10.4.3. Tertiary Efficacy Measures

The RUD Lite and the EQ-5D will be summarized descriptively by treatment. Treatment comparisons between RVT-101 and placebo will be analyzed using an analysis of covariance (ANCOVA) model. Details will be provided in the SAP.

10.4.4. Responder Analysis

In this trial the following responder definitions will be presented:

1. ADAS-Cog-11: Improvement by at least 3 points from baseline at Week 24
2. ADCS-ADL: No change or improvement from baseline at Week 24
3. CIBIC+: No change or improvement at Week 24
4. ADAS-Cog-11 composite: Simultaneously meeting the criteria for ADAS-Cog-11, CIBIC+, and ADCS-ADL

Alternative composite endpoints and definitions of responders may be explored. The percentage of responders and the difference in proportions compared to placebo will be presented. This data will be analyzed using logistic regression or Cochran–Mantel–Haenszel test. Further details will be given in the SAP.

10.4.5. Pharmacokinetic Analyses

Plasma concentrations will be listed and summarized by study visit and treatment group.

Pharmacokinetic parameters for RVT-101 (AUC_{TSS} , C_{max-ss} and C_{min-ss}) for each subject will be estimated via nonlinear mixed effect modeling using a population PK model based on data from previous studies.

No population PK analysis is planned for donepezil. Donepezil concentrations will be visually compared to literature steady state values (mean \pm SD) (Tiseo et al, 1998):

$$5 \text{ mg } C_{min} = 21.4 \pm 3.8 \text{ and } C_{max} = 34.1 \pm 7.3 \text{ ng/mL}$$

$$10 \text{ mg } C_{min} = 38.5 \pm 8.6 \text{ and } C_{max} = 60.5 \pm 10.0 \text{ ng/mL,}$$

where C_{min} is the minimum (trough) concentration and C_{max} is the peak concentration

10.4.6. Pharmacokinetic / Pharmacodynamic Analyses

Relationships between RVT-101 PK parameters and measures of safety and efficacy will be explored.

10.4.7. Safety Analyses

The safety analyses will be based on the Safety Population.

Safety will be assessed by summarizing and analyzing AEs, laboratory analytes, vital signs, ECG parameters, physical examination findings, C-SSRS scores, and concomitant medications.

10.4.7.1. Adverse Events

AEs will be considered treatment-emergent (TEAEs) if they start or worsen after first dose of the double-blinded treatment. If an AE begins or worsens on the first day of investigational product administration, a CRF and source data note will be provided to clarify whether it occurred prior to or after investigational product administration. TEAEs, SAEs including deaths, AEs that lead to discontinuation of investigational product, and AEs by maximum severity and relationship to investigational product will be summarized by MedDRA system organ class (SOC) and preferred term. TEAEs will also be summarized by preferred term, sorted by decreasing frequency within SOC. AEs will be summarized separately for the Single-Blind Run-In Period, the Double-Blind Treatment Period, and the Follow-up Period.

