7.8. Treatment after the End of the Study

The investigator is responsible for ensuring that consideration has been given to the post-study care of the subject's medical condition.

After completion of Visit 8, the subject may be considered for enrollment in the open-label extension study RVT-101-3002. Only subjects who do not enroll in the extension study will complete the Follow-up Visit (Visit 9).

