Throughout the Baseline and Double-Blind Treatment Periods, all clinic visits will be scheduled according to specified visit windows, and all specified assessments will be completed (Table 2). The administration of the ADAS-Cog should be kept within a ± 1-hour window of the time of day of the Baseline assessment for each subject to diminish the potential impact of circadian fluctuations in cognition. This should be taken into consideration when scheduling and performing baseline ADAS-Cog assessments.

The order of assessments should remain consistent during the Double-Blind Treatment Period, and when possible, the ADAS-Cog should be given to the subject first, followed by the other efficacy endpoint scales. If possible, other assessments, including ECG, vital signs, and blood draws, should be performed after cognitive testing and other endpoint scales. When possible ADCS-ADL should be given as the first assessment to the caregiver followed by other endpoint scales.

Although caregiver and subject visits are recommended to be on the same day, this is not required so long as they are each kept within the specified visit window. However, every effort should be made to have the same caregiver throughout the study.

Subjects who prematurely discontinue double-blind investigational product should be encouraged to return to the clinic for an Early Termination Visit, and the early termination procedures should be performed as indicated in the time and events schedule.

Safety Follow-Up: All subjects who complete the Double-Blind Treatment Period and do not enter the open-label extension study RVT-101-3002 will be required to attend a Safety Follow-Up clinic visit (Visit 9) 14 to 19 days after the last day of treatment.

Table 2. Time and Events Schedule

Study Period: Study Visit Number:	Screening V1	Run-in V2	Baseline V3 ¹	Treatment						Follow-up ¹¹ V9	ET
				V4	V5	V6	V7	V8	V9		
Study Week:	W(-7)	W(-3)	W0	W3	W6	W12	W18	W24	W26	ET	
Study Day: relative to Baseline unless specified	Up to 28 days before V2	21 + 5 days ^{1,2} before V3	0	21 ± 3	42 ± 3	84 ± 5	126 ± 5	168 ± 5	14 to 19 days after last dose of IP		
Informed consent	X										
Inclusion and exclusion criteria	X		X								
Demography	X										
Medical history	X										
Concomitant medications review	X	X	X	X	X	X	X	X	X	X	
Urine drug screen	X										
C-SSRS	X		X	X	X	X	X	X	X	X	
Randomization			X								
Dispense investigational product ³		X	X								
Dispense study-supplied donepezil ³		X	X								

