9. If these tests were performed within 12 months prior to the planned first dose of investigational product, testing is not required. Records must be present in the subject's source documents.
10. All PK blood samples should be taken after cognitive testing, ECG, and vital signs measurements have been performed except for the Week 12 (V6) sample, which should be taken prior to dosing in the clinic.
11. Required only for subjects who do not enter the open-label extension study RVT-101-3002.

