10.3. Data Analysis Considerations

10.3.1. Analysis Populations

The ITT Population will consist of all subjects randomized to treatment who have taken at least 1 dose of investigational product and who have at least 1 post-baseline assessment. This will be the primary population used for the efficacy analysis.

The Per-Protocol (PP) Population will consist of those members of the ITT Population who have no major protocol violations. The PP Population will not be analyzed if this population comprises more than 95% or less than 50% of the ITT Population. This population will be used for confirmatory analysis of the 2 primary efficacy variables and other cognitive and functioning endpoints. The PP Population will be identified prior to breaking the study blind.

The primary population for safety analyses will be the Safety Population, which will consist of all subjects who were randomized and took at least 1 dose of investigational product.

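### Under the blanket Safety Population rule, Follow-up Period adverse event percentages would count extension entrants who have no Follow-up Visit, and the Run-In summary would omit dosed subjects who were never randomised.

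*Protocol*

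**What the plan says.** **Analysis set.** Protocol 10.4.7 gives one general rule: "The safety analyses will be based on the Safety Population". Section 10.3.1 defines that population as "all subjects who were randomized and took at least 1 dose of investigational product".

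**Tables.** Section 10.4.7.1 adds: "AEs will be summarized separately for the Single-Blind Run-In Period, the Double-Blind Treatment Period, and the Follow-up Period". Section 10.4 sets the format: "Categorical data will be summarized by counts and percentages". No section names a separate denominator for any of the three periods.

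**Who is followed.** Footnote 11 to the Time and Events Schedule (Table 2) marks the follow-up column: "Required only for subjects who do not enter the open-label extension study RVT-101-3002". Section 7.8 agrees. The text of 8.1 says "All subjects who complete the Double-Blind Treatment Period and do not enter the open-label extension study RVT-101-3002 will be required" to attend Visit 9, at 14 to 19 days after treatment ends. That sentence covers completers and does not mention subjects who stop early. Section 6.6.1 keeps collecting adverse event information after discontinuation, and 8.3.2.1.3 ends routine collection at the follow-up contact.

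**Who is dosed in run-in.** All subjects entering run-in take single-blind placebo (7.3). Under 8.2, some are then not randomised because their MMSE moved by more than 3 points or left the range 10–26.

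**SAP.** The supplied SAP is an addendum on estimands, imputation and responders. It does not address adverse event denominators.

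**The concern.** In the Follow-up Period table, a rollover subject can never enter the numerator but, under the general rule, sits in the denominator. The printed percentage is then the event risk among followed subjects multiplied by the share of the Safety Population that was followed. That share is set by willingness to enter the extension, not by safety. Two consequences follow:

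- Both arms' percentages are too low whenever rollover is above zero.
- If rollover differs by arm, equal risks print as unequal percentages, or a true difference is masked.

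The Run-In table has the opposite fault: the population is too narrow. A subject who took run-in product and left before randomisation is not a screen failure under 6.5, because the subject entered run-in, and is not in the Safety Population, because the subject was not randomised. An adverse event that ended participation during run-in would therefore be missing from the run-in summary.

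**Working it through.** The plan states no figure on this point, so there is none to reproduce. The calculation below is illustrative.

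**Inputs from the documents**
- Randomised: about 1150, or 575 per arm (Protocol 10.2 and synopsis).
- Drop-out *d*: at most 11% (SAP addendum 3.2.3.1). The planning figure was about 25%, including missing data (Protocol 10.2).

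**Assumptions, not in the documents**
- Rollover *r*, as a share of completers: 10% to 90%.
- Event risk among followed subjects: 5%, equal in both arms.
- Early terminators: either none or all have follow-up observation, because 8.1 and 6.6.1 leave this open.

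**Formulas**
- Observed share, early terminators not followed: (1 − d)(1 − r)
- Observed share, early terminators followed: (1 − d)(1 − r) + d
- Printed percentage = risk × observed share

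**Dilution at d = 0.11**

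| Rollover r | Observed share | 5% risk prints as |
|---|---|---|
| 10% | 0.801–0.911 | 4.0–4.6% |
| 25% | 0.668–0.778 | 3.3–3.9% |
| 50% | 0.445–0.555 | 2.2–2.8% |
| 80% | 0.178–0.288 | 0.9–1.4% |
| 90% | 0.089–0.199 | 0.4–1.0% |

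At 50% rollover: 0.89 × 0.5 = 0.445, and 0.445 + 0.11 = 0.555. Of 1150 subjects, that is 512 to 638 observed.

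Not all of the shortfall is due to rollover. At r = 10% with early terminators unobserved, the shortfall is 1 − 0.801 = 19.9%. Rollover supplies 0.89 × 0.10 = 8.9 points and drop-out the other 11. With early terminators followed, only the 8.9 points remain.

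**Sensitivity to drop-out.** At d = 0.25 and r = 50%, the share is 0.75 × 0.5 = 0.375, or 0.625 with early terminators followed. At d = 0 it is 0.50.

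**Arms with equal risk but different rollover (assumed 75% and 85%, d = 0.11)**
- Early terminators not followed: 0.89 × 0.25 = 0.2225 and 0.89 × 0.15 = 0.1335. A 5% risk prints as 1.11% and 0.67%, a ratio of 1.67.
- Early terminators followed: 0.3325 and 0.2435. It prints as 1.66% and 1.22%, a ratio of 1.37.
- Equal rollover and equal drop-out: the ratio is 1, but both percentages remain too low.

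**After the fix.** With followed subjects as denominator, the assumed 5% prints as 5% in both arms at any rollover.

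**Run-in.** The documents give no run-in attrition or run-in event rate, so no size can be attached, and the direction of the error in the run-in percentage is not determined either.

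**The case against.** **The denominator is implied, not written.** Section 10.4.7.1 gives no N for any period table, and naming an analysis set does not by itself forbid an at-risk subset of it. A reader might infer that the plan expressly puts the whole Safety Population under the follow-up percentages. It does not; that is what the general rule yields when nothing else is said. This stands as a limit on the point.

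**The relevant detail may exist elsewhere.** Section 10.4 describes key elements and repeatedly defers to the SAP. The addendum refers to a final SAP dated August 9, 2017, which is not among the documents reviewed and may define the denominators. This also stands, and makes the request conditional.

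**This is not the only view of events after treatment stops.** A reader might infer that it is. But 6.6.1 continues adverse event collection after discontinuation, 6.6.2 calls for an Early Termination Visit, 8.3.2.1.3 requires reporting of serious events that come to light up to 30 days after the last dose, and the treatment-emergent definition in 10.4.7.1 has no end date. The Follow-up table is only the one separate tabulation of that period that the documents specify.

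**The size is assumed.** A reader might take the ratios above as a forecast. They show what unequal rollover would do; nothing in the documents says that rollover differs by arm.

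**A new denominator does not restore randomisation.** Subjects who decline the extension select themselves after randomisation. That is correct, and is why the table should be labelled descriptive. It is no reason to keep a denominator that includes subjects who could not be observed.

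**The run-in gap is small.** Everyone in run-in is on placebo, so no comparison of drug with placebo is touched. Agreed; the gap affects the completeness of that table only.

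**Conclusion.** The point holds as a minor correction to two descriptive safety tables. Applied as written, the rule in 10.4.7 makes Follow-up Period percentages too low by the unobserved fraction at any rollover above zero, and leaves dosed but non-randomised subjects out of the Run-In summary. The dilution follows from the protocol's own visit rules; its amount does not. The observed share of about 45–55% rests on an assumed 50% rollover, the addendum's 11% ceiling for drop-out, and the open question of whether early terminators are followed. A difference between arms is a possibility only.

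A reader might extend the concern to the main safety results or to efficacy. The documents do not support that: the Safety Population is the right denominator for the Double-Blind Treatment Period, and no hypothesis test is specified for the Follow-up or Run-In tables. If the final SAP already defines at-risk denominators by period, confirming this closes the point.

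**What to change.** Unless the final SAP already does so, add to Protocol 10.4.7.1 or the SAP:

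- **Follow-up Period:** the denominator, by arm, is Safety Population subjects who did not enter RVT-101-3002 and had at least one follow-up contact after treatment. State whether early terminators count. Show that N in the column header and the number rolling over in each arm. Footnote that the comparison is descriptive and not fully randomised.
- **Run-In Period:** the denominator is all subjects who took at least one dose of run-in product, whether or not later randomised. Those not randomised have no arm, so an overall column is needed.
- **Double-Blind Treatment Period:** keep the Safety Population.

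The cost is a few sentences and two denominators in table programming, with no new data. The follow-up columns will have smaller Ns and less precise percentages, which reflects how many subjects were actually observed.

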10.4.7.2. Clinical Laboratory Tests

Summaries of clinical laboratory data will be provided for subjects in the Safety Population. No inferential statistics will be provided.

Quantitative values and change from baseline in quantitative values will be summarized by planned nominal time and treatment for each quantitative laboratory value. Listings of all laboratory results and reference ranges will be provided. For multiple lab assessments at the same time point, the worst value will be used for the data summaries.

Laboratory values that fall outside of the reference range will be flagged as H=High or L=low. A lab shift table may be provided to show the baseline to the worst post value. Laboratory values that do not meet the laboratory abnormalities will be assigned N=normal in the shift table.

10.4.7.3. Vital Signs, Electrocardiograms, Physical Findings, and Other Safety Evaluations

Descriptive summaries of medical history, vital signs, weight, and ECG parameters will be presented separately for each study visit and treatment group. Clinically significant abnormal morphological ECG findings will be summarized by study visit.

Abnormal physical examination findings will be summarized to include the number and percentage of subjects experiencing each treatment-emergent abnormal physical finding.

Concomitant medications will be coded using the WHO ATC classification (http://www.whocc.no/filearchive/publications/1_2013guidelines.pdf).

These data will be summarized by treatment group.

10.4.7.4. Suicidality

A subject data listing of all answers of the C-SSRS questionnaire will be presented. The number and percentage of subjects reporting suicidal ideation and behavior will be summarized. Additional summaries may be provided if data warrant. Details will be provided in the SAP.

10.4.8. Subgroup Analyses

The efficacy analyses will be performed for the following subgroups:

- Milder Population (Baseline MMSE 16-26)
- Moderate Population (Baseline MMSE 10-20)
- Female
- Male

Analyses of additional subgroups based on demographics and baseline characteristics will be described in the SAP.

10.4.9. Other Analyses

Additional analyses of the data may be conducted as deemed appropriate and will be detailed in the SAP. Further analyses of the data not specified in the SAP may be undertaken as post-hoc analyses after completion of the study. Results of all study assessments will be included in an appendix to the study report.

11. RESPONSIBILITIES

11.1. Investigator Responsibilities

11.1.1. Good Clinical Practice

The investigator will ensure that this study is conducted in accordance with the principles of the “Declaration of Helsinki” (as amended in Edinburgh, Tokyo, Venice, Hong Kong, and South Africa), International Conference on Harmonisation (ICH) guidelines, or with the laws and regulations of the country in which the research is conducted, whichever affords the greater protection to the study subject. The investigator will ensure that the basic principles of “Good Clinical Practice,” as outlined in 21 Code of Federal Regulations (CFR) 312, subpart D, “Responsibilities of Sponsors and Investigators,” 21 CFR, part 50, 1998, and 21 CFR, part 56, 1998, are adhered to. These standards are consistent with the requirements of the European Community Directive 2001/20/EC, which shall be adhered to.

Since this is a “covered” clinical trial, the investigator will ensure that 21 CFR, Part 54, 1998, is adhered to; a “covered” clinical trial is any “study of a drug or device in humans submitted in a marketing application or reclassification petition subject to this part that the applicant or FDA relies on to establish that the product is effective (including studies that show equivalence to an effective product) or that make a significant contribution to the demonstration of safety.” This requires that investigators and all sub-investigators must provide documentation of their financial interest or arrangements with Axovant Sciences, or proprietary interests in the drug being studied. This documentation must be provided before participation of the investigator and any sub-investigator. The investigator and sub-investigator agree to notify Axovant Sciences of any change reportable interests during the study and for 1 year following completion of the study. Study completion is defined as the date that the last subject has completed the protocol defined activities.

This study is also subject to and will be conducted in accordance with 21 CFR, part 320, 1993, “Retention of Bioavailability and Bioequivalence Testing Samples.”

11.1.2. Institutional Review Board/Independent Ethics Committee Approval

This protocol and any accompanying material to be provided to the subject and caregiver (such as advertisements, subject information sheets, or descriptions of the study used to obtain informed consent) will be submitted by the investigator to an IRB or IEC. Approval from the IRB or IEC must be obtained before starting the study and should be documented in a letter to the investigator specifying the protocol number, protocol version, protocol date, documents reviewed, and date on which the committee met and granted the approval.

Any modifications made to the protocol or other documents described in the above paragraph after receipt of IRB or IEC approval must also be submitted to the IRB or IEC for approval before implementation.

11.1.3. Informed Consent

The investigator is responsible for obtaining written informed consent from each individual participating in this study after adequate explanation of the aims, methods, objectives, and potential hazards of the study and before undertaking any study-related procedures. The investigator must utilize an IRB- or IEC-approved consent form for documenting written informed consent. Each informed consent will be appropriately signed and dated by the subject or the subject's legally authorized representative and the person obtaining consent. Consent from both the caregiver representative and subject will be obtained.

